5.1. ADVERSE EVENTS

5.1.1. Definitions

An AE is defined as any undesired medical occurrence in a patient or clinical investigation patient receiving a pharmaceutical product regardless of a causal relationship with this treatment. An AE can therefore be any unfavorable sign and unintended sign (including an abnormal laboratory finding), symptom, or disease temporarily associated with the use of a study treatment, whether or not related to the study treatment.

AE observation period

- Pre-treatment AEs are AEs that developed or worsened or became serious from the signed informed consent up to first dose of study treatment.
- ***Treatment-emergent adverse events (TEAE)*** are defined as any AE that developed or worsened or became serious during the treatment period (time from first dose of study treatment to last dose of study treatment + 30 days inclusive); or any AE with a start date after the first dose of study treatment, and is considered related to study treatment by the Investigator. Note that any AE that was present at baseline but worsened in toxicity grade after first dose of study treatment, and is subsequently considered as related to study treatment shall be considered as TEAE.
- Post-treatment AEs are AEs that developed or worsened or became serious during post-treatment period and is not considered TEAE.

All AEs (including serious adverse events [SAEs]) will be coded to a PT and associated primary SOC using the MedDRA version 20.1.

The severity of all AEs will be graded according to the CTCAE Grading Scale. An AE with a CTCAE grade of 3 or higher is considered a severe AE. The severity of the AE is different from the seriousness of the AE which is defined below. For AEs not covered by CTCAE, the severity will be characterized as “mild,” “moderate,” or “severe” according to the following definitions:

- Mild events are usually transient and do not interfere with the patient’s daily activities.
- Moderate events introduce a low level of inconvenience or concern to the patient and may interfere with daily activities.
- Severe events interrupt the patient’s usual daily activities.

Serious adverse events

A SAE is any untoward medical occurrence that occurs at any dose (including after the informed consent form is signed and prior to dosing) that:

- Results in death
- Is life-threatening (patient is at immediate risk of death from the event as it occurred)
- Requires in-patient hospitalization (formal admission to a hospital for medical reasons) or prolongation of existing hospitalization
- Results in persistent or significant disability/incapacity
- Results in a congenital anomaly/birth defect

SAE needs to be clearly documented on the patient’s AE form.

5.1.2. Analysis Methods

The primary focus of AE reporting will be on TEAEs. Pre- and post-treatment AEs will be described separately.

If an AE date/time of onset (occurrence, worsening, or becoming serious) is incomplete, an imputation algorithm will be used to classify the AE as pre-treatment, treatment-emergent, or post-treatment. The algorithm for imputing date/time of onset will be conservative and will classify an AE as treatment-emergent unless there is definitive information to determine it is

pre-treatment or post-treatment. Details on classification of AEs with missing or partial onset dates are provided in Section 2.2.2.

AE summaries will include number (n) and percentage (%) of patients experiencing an AE. The denominator for computation of percentages is the number of patients in the corresponding population.

Unless otherwise specified, sorting order will follow the alphabetic order in SOC, and further by decreasing number of events in PTs within each SOC. When more than one PT has same number of events, the order of presentation will be alphabetical in PTs.

Multiple occurrences of the same event in the same patient will be counted only once in the tables.

Based on the entries on the eCRF AE page,

- An AE is considered potentially related to study treatment if:
 - the entry for “Relationship to selinexor” is either “Possibly Related” or “Related”, or
 - the entry for “Relationship to Dexamethasone” is either “Possibly Related” or “Related”.
- An AE is considered potentially related to selinexor if the entry for “Relationship to selinexor” is either “Possibly Related” or “Related”.
- An AE is considered potentially related to dexamethasone if the entry for “Relationship to Dexamethasone” is either “Possibly Related” or “Related”.

5.1.2.1. Analysis of TEAEs

An overview table summarizing the following will be presented:

- TEAEs
- TEAEs with CTCAE Grade 3 and 4
- Serious TEAEs
- TEAE leading to dose modification in selinexor, i.e., dose reduction or interruption in selinexor
- TEAEs leading to permanent treatment discontinuation
- TEAEs leading to death

- Treatment-related adverse events (TRAEs), i.e., TEAEs potentially related to either selinexor or dexamethasone
- Serious TRAEs
- TRAE leading to dose modification in selinexor, i.e., dose reduction or interruption in selinexor
- TRAEs leading to permanent treatment discontinuation
- TRAEs leading to death

TEAEs will be summarized by primary SOC and PT and will include the following categories:

- All TEAEs
- All TEAEs, by relatedness
 - TEAEs potentially related to either selinexor or dexamethasone
 - TEAEs potentially related to selinexor only
 - TEAEs potentially related to dexamethasone only
 - TEAEs not related to selinexor or dexamethasone
- All TEAEs, by maximum grade
- Grade 3 or higher TEAEs
- Grade 3 or higher TEAEs, by relatedness
 - Grade 3 or higher TEAEs potentially related to either selinexor or dexamethasone
 - Grade 3 or higher TEAEs potentially related to selinexor only
 - Grade 3 or higher TEAEs potentially related to dexamethasone only
 - Grade 3 or higher TEAEs not related to selinexor or dexamethasone
- TEAEs leading to selinexor dose reduced or drug interrupted
- TEAEs leading to dexamethasone dose reduced or drug interrupted
- Grade 3 or higher TEAEs leading to selinexor dose reduced or drug interrupted
- TEAEs leading to withdrawn from selinexor treatment
- Grade 3 or higher TEAEs leading to withdrawn from selinexor treatment

The most commonly reported (at least 10% of all patients) TEAEs will be presented by PT only and will include the following categories:

- The most commonly reported TEAEs
- The most commonly reported TEAEs potentially related to study treatment

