2.2.5. Handling of Missing Assessment of Relationship of AEs to Study Treatment

If the assessment of the relationship to study treatment is missing, then the relationship to study treatment in the frequency tables is considered as possibly related, but no imputation should be done at the data level or in data listings.

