5.1.2.2. Analysis of SAEs

Treat-emergent SAEs will be summarized by primary SOC and PT and will include the following categories:

- All treatment-emergent SAEs
- Treatment-emergent SAEs, by relatedness
 - Treatment-emergent SAEs potentially related to either selinexor or dexamethasone
 - Treatment-emergent SAEs potentially related to selinexor only

- Treatment-emergent SAEs potentially related to dexamethasone only
- Treatment-emergent SAEs not related to selinexor or dexamethasone
- Treatment-emergent SAEs leading to selinexor dose reduced or drug interrupted
- Treatment-emergent SAEs leading to dexamethasone dose reduced or drug interrupted
- Treatment-emergent SAEs leading to withdrawal from selinexor treatment

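### No listed adverse event table reports the selinexor-related incidence as SAP 5.1.2 defines it, because the by-drug rows are labelled 'only'

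*SAP*

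**What the plan says.** SAP 5.1.2 works from two separate eCRF fields, one per drug. For selinexor: "An AE is considered potentially related to selinexor if the entry for “Relationship to selinexor” is either “Possibly Related” or “Related". For dexamethasone: "An AE is considered potentially related to dexamethasone if the entry for “Relationship to Dexamethasone” is either “Possibly Related” or “Related". Neither definition looks at the other drug's field, so one event can meet both. An event related to study treatment is one that meets at least one of them.

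SAP 5.1.2.1 then splits all TEAEs by relatedness into "TEAEs potentially related to either selinexor or dexamethasone", "TEAEs potentially related to selinexor only", "TEAEs potentially related to dexamethasone only" and a row for events related to neither drug. The same four rows recur for Grade 3 or higher TEAEs. SAP 5.1.2.2 repeats them for serious events, for example "Treatment-emergent SAEs potentially related to selinexor only".

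SAP 5.1.2 also states that the summaries give numbers and percentages of patients, and that repeated occurrences of one event in a patient count once. The word 'only' is not defined.

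**The concern.** The SAP defines a category for the investigational drug and then, on the plain wording, never tabulates it. The sole by-relatedness row naming selinexor alone leaves out events also attributed to dexamethasone. The row that keeps those events mixes them with events attributed to dexamethasone alone.

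Dexamethasone is given with each selinexor dose (Protocol 11.1.3), so an investigator can attribute an event to both. The protocol's dose-modification guidance (11.1.5) distinguishes selinexor-related events from others, and the report of the primary analysis precedes a planned New Drug Application (SAP 1.6). A reader of that report will look for the selinexor-related incidence of TEAEs, Grade 3 or higher TEAEs and serious events. The listed tables would not give it.

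**Working it through.** The plan states no figure to reproduce. The check sets the definitions against the table rows, then asks whether the missing figure can be recovered.

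**Step 1. Where each event goes.** 'Yes' means possibly related or related; 'only' is read as exclusive.

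| Selinexor entry | Dexamethasone entry | Meets the 5.1.2 selinexor definition | Rows in which it counts |
|---|---|---|---|
| yes | no | yes | either; selinexor only |
| yes | yes | yes | either |
| no | yes | no | either; dexamethasone only |
| no | no | no | not related |

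The selinexor-related class is the first two lines together. No row holds exactly those two.

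**Step 2. All related-AE outputs listed.**

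- All TEAEs and Grade 3 or higher TEAEs by relatedness (SAP 5.1.2.1), and serious events by relatedness (SAP 5.1.2.2): the four rows above.
- Overview table, including related events that are serious, fatal, or lead to selinexor dose modification or treatment discontinuation (SAP 5.1.2.1): union of the two drugs.
- Most commonly reported related TEAEs (SAP 5.1.2.1): study treatment, which is the union.
- Related fatal TEAEs (SAP 5.2): union.
- Protocol 13.3.7.1: relatedness to treatment as a whole, not by drug.

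None carries the 5.1.2 selinexor class, and none has a row for events related to both drugs.

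**Step 3. Can it be recovered?** At event level, selinexor-related = 'either' − 'dexamethasone only'. The tables count patients, and one patient can have episodes with different attributions. Let E, S₀ and D₀ be the patients under 'either', 'selinexor only' and 'dexamethasone only', and S the patients meeting the selinexor definition.

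- A patient in E but not in D₀ has a related episode, and it must involve selinexor. So S ≥ E − D₀.
- Every patient in S₀ is in S, so S ≥ S₀.
- Every patient in S is in E, so S ≤ E.

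Take E = 10, S₀ = 4, D₀ = 4. The lower bound is the larger of 10 − 4 = 6 and 4, that is 6; the upper bound is 10. Three patient mixes give these same rows:

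| Mix of patients | E | S₀ | D₀ | S |
|---|---|---|---|---|
| 4 selinexor only, 4 dexamethasone only, 2 both | 10 | 4 | 4 | 4 + 2 = 6 |
| 2 with one episode of each single attribution, 2 selinexor only, 2 dexamethasone only, 4 both | 10 | 4 | 4 | 2 + 2 + 4 = 8 |
| 4 with one episode of each single attribution, 6 both | 10 | 4 | 4 | 4 + 6 = 10 |

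The rows do not determine S. The same holds at system organ class level, where one patient can contribute different terms with different attributions.

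**Step 4. Size.** The documents give no split by drug, so this is arithmetic on an assumption, not an estimate. Protocol 4.3.1.4 reports treatment-related fatigue in 64% of 92 patients (0.64 × 92 = 58.9, about 59). Assume that all of it is selinexor-related, with one attribution per patient, and that a fraction q is also attributed to dexamethasone. The 'selinexor only' row would show 64% × (1 − q): 64%, 48%, 32% and 16% for q = 0, 0.25, 0.50 and 0.75. The rate under the 5.1.2 definition stays at 64% throughout.

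**The case against.** The best defence is that 'only' is a loose label. SAP 5.1.2 defines three classes (study treatment, selinexor, dexamethasone), and the three related rows match them in number and order. No other listed table uses the single-drug definitions, and no exclusive class is defined anywhere. The sponsor may have meant the inclusive class. That is possible, but the SAP does not say so. Beside 'either' and 'not related', the word reads as exclusive, and a programmer following it would drop events attributed to both drugs. The text needs correcting on either reading.

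It is also fair that the protocol requires only relatedness to treatment as a whole, which 'either' supplies. By-patient listings (Protocol 13.3 and 13.3.7.1) keep the underlying data, and the bounds are close together when few patients have dexamethasone-only events. All of this stands and limits the point. It does not supply the row that the SAP defines.

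A reader might infer more than the documents support:

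- **That the missing-causality rule makes this worse.** SAP 2.2.5 says "the relationship to study treatment in the frequency tables is considered as possibly related", but it applies when the assessment for study treatment is missing. It does not say that one blank drug field is imputed when the other is completed.
- **That attribution to both drugs is common.** The documents give no data. Protocol Section 1 lists fatigue and nausea among selinexor's frequent effects and describes dexamethasone as preventing them, which if anything argues against it for those terms.
- **That the 'only' rows are the sole selinexor-specific outputs.** The SAP also tabulates events leading to selinexor reduction, interruption or withdrawal, irrespective of causality.

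**Conclusion.** The point holds, within limits. On the plain wording, no listed table gives the incidence of selinexor-related TEAEs, Grade 3 or higher TEAEs or serious events as SAP 5.1.2 defines it, and patient-level rows allow only bounds.

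It would be tempting to conclude that the study report understates selinexor toxicity. The documents do not support that. The headline related-AE outputs use the union, which can only equal or exceed the selinexor-related rate, and events attributed to both drugs stay visible under 'either'. The defect is confined to the drug-specific rows of descriptive safety tables; the primary response-rate analysis is untouched. Its size is unknown and is zero if no event is attributed to both drugs. The conclusion rests on reading 'only' as exclusive. If it was meant inclusively, the fault is the label.

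**What to change.** In SAP 5.1.2.1 (all TEAEs and Grade 3 or higher TEAEs) and SAP 5.1.2.2 (serious events), replace the two 'only' rows with 'potentially related to selinexor' and 'potentially related to dexamethasone', or add these beside them. Define each exactly as in 5.1.2 and state that it applies regardless of the other drug's entry. Keep 'either' and 'not related'. A 'both' row is optional. If the 'only' rows stay, define 'only'.

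The cost is SAP wording and a small change to a table-program filter. Causality is already recorded per drug, so no new data are needed. The selinexor row will be the same as, or somewhat higher than, the 'selinexor only' row.

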5.1.2.2. Analysis of SAEs

Treat-emergent SAEs will be summarized by primary SOC and PT and will include the following categories:

- All treatment-emergent SAEs
- Treatment-emergent SAEs, by relatedness
 - Treatment-emergent SAEs potentially related to either selinexor or dexamethasone
 - Treatment-emergent SAEs potentially related to selinexor only

- Treatment-emergent SAEs potentially related to dexamethasone only
- Treatment-emergent SAEs not related to selinexor or dexamethasone
- Treatment-emergent SAEs leading to selinexor dose reduced or drug interrupted
- Treatment-emergent SAEs leading to dexamethasone dose reduced or drug interrupted
- Treatment-emergent SAEs leading to withdrawal from selinexor treatment

5.2. DEATH

The following summaries on death events will be provided:

- An overview of all death events and primary cause of death
- TEAEs leading to death (death as an outcome on the AE report page as reported by the Investigator), by primary SOC and PT
- TEAEs leading to death and are potentially related to selinexor or dexamethasone, by primary SOC and PT
- Listing of all death events

5.3. LABORATORY SAFETY VARIABLES

5.3.1. Definitions

Clinical laboratory data consists of blood analysis, including hematology, serum chemistry, coagulation parameters, and urinalysis. Clinical laboratory values in conventional units will be converted using the international system of units (SI).

Blood samples for clinical laboratory tests will be taken as specified in the study protocol. The laboratory parameters will be classified as follows:

- Hematology (blood sample: ethylenediaminetetraacetic acid [EDTA]) tests including hemoglobin, hematocrit, mean corpuscular volume, mean corpuscular hemoglobin, mean corpuscular hemoglobin concentration, white blood cell (WBC) count, WBC differential, red blood cell count, lymphocytes, monocytes, neutrophils, eosinophils, basophils, and platelets. WBC differential may be automated or manual as per institutional standards.
- Serum Chemistry (blood sample: serum)
 - Complete Serum Chemistry will include sodium, potassium, chloride, bicarbonate (HCO_3^-), blood urea nitrogen (BUN), creatinine, glucose, calcium, phosphate, magnesium, alanine aminotransferase (ALT), aspartate aminotransferase (AST), alkaline phosphatase, total bilirubin and lactate dehydrogenase (LDH), total protein, albumin, amylase, lipase, creatine kinase and uric acid.
 - Limited Serum Chemistry will include sodium, potassium, chloride, bicarbonate, BUN, creatinine, glucose, ALT, AST, alkaline phosphatase, total bilirubin and LDH, unless otherwise clinically indicated.
- Thyroid-stimulating hormone (TSH)

- Coagulation parameters will include prothrombin time, international normalization ratio (INR), and activated partial thromboplastin time (aPTT).
- Urinalysis will include appearance, color, urine bilirubin, glucose, hemoglobin, ketones, pH, protein, specific gravity, and urobilinogen. Microscopy will only be performed if clinically indicated.

5.3.2. Analysis of Laboratory Variables

Whenever applicable, severity of selected clinical laboratory measures will be determined based on the CTCAE criteria. The worst toxicity grade in hematology and chemistry will be summarized by toxicity grade. Shift tables that present changes from baseline to worst on-study and baseline to last on-study values relative to CTCAE classification ranges will be presented.

For several key laboratory parameters (e.g., sodium, creatinine, platelet, hemoglobin, WBC, BUN-to-creatinine ratio, urea-to-creatinine ratio), box plots on measurements over time may be presented.

A listing of possible Hy's law cases (ALT or AST > 3 x upper limit of normal [ULN] with simultaneous total bilirubin > 2 x ULN) will be presented. The elevations of ALT/AST and total bilirubin must occur within 2 days of each other.

Thresholds/Range analyses for selected laboratory, vital signs, and ECG parameters will be conducted. Please refer to Appendix 7.2 for the definitions on thresholds/ranges for selected parameters. The number and percentage of patients classified into each category based on worst values will be presented.

5.4. VITAL SIGNS, ECOG, AND PHYSICAL EXAMINATION VARIABLES

Full physical examinations with vital signs are performed only during screening and end-of-treatment (EoT) visits, including height (without shoes) in centimeters (cm) [measured during screening visit only], weight (indoor clothing without shoes) in kilograms (kg), temperature, heart rate, systolic and diastolic blood pressure, and oxygen saturation.

At other visits, symptom-directed physical examinations are conducted with vital signs (temperature, heart rate, systolic and diastolic blood pressure).

An ECOG score assessment with grades 0-5 will be performed during screening, day 1 of each cycle, and the EoT visit.

Shift tables that present changes from baseline to worst on-study and last on-study for systolic blood pressure, diastolic blood pressure, and ECOG performance status values will be produced.

Abnormal vital signs results will be summarized in the threshold/range analyses as defined in Appendix 7.2.

5.5. ELECTROCARDIOGRAM (ECG)

Standard 12-lead ECGs will be performed during screening and EoT visits. Patients must rest for at least 5 minutes prior to the ECG recording. The Investigator will interpret the ECG using one of the following categories: normal, abnormal but not clinically significant, or abnormal and clinically significant. The following will be assessed: heart rate, rhythm, interval from start of

the Q wave to the end of the S wave (QRS), interval from the beginning of the P wave until the beginning of the QRS complex (PR Interval), interval between the start of the Q wave and the end of the T wave (QT), and QT corrected (QTc) using Bazett's formula or calculated by the Fridericia correction formula (*Bazett 1920, Fridericia 1920*). If Bazett correction is entered by the site, the Fridericia corrected QTc interval (QTcF) will be derived using the formula: $QT/(RR^{1/3})$, where $RR = 60/\text{heart rate}$.

Abnormal ECG results will be summarized in the threshold/range analyses as defined in Appendix 7.2.

5.6. OPTHALMIC EXAM

A full ophthalmic examination will be performed during the Screening and EoT visits. Prior to dilation, best corrected visual acuity (Snellen's Equivalent based on either Snellen chart or Early Treatment Diabetic Retinopathy Study [ETDRS chart]), and slit lamp examination including tonometry will be conducted. Following dilation, funduscopy will be conducted. Please refer to Protocol v5.0 for details on the grading of cataract if seen during the examination.

All ophthalmic examination findings will be presented in a data listing.

7. APPENDICE

7.1. Appendix I: Schedule of Assessments

Table 7-1 Schedule of Assessments and Study Activities

Activity/Assessment	Screening	Cycle 1				Cycle 2		Cycles \geq 3	End-of-Treatment (EoT) Visit	Safety Follow-up Call	Durability of Response and Survival Follow-up ¹⁵
	Day -21 to Day -1	Day 1	Day 3 ¹⁴	Day 8	Day 15	Day 1	Day 15	Day 1	\leq 14 Days Post Last Dose	30 Days Post-Last Dose	Every 3 mo.
		-1 day	+1 day	\pm 1 day	\pm 1 day	\pm 2 days	\pm 2 days	\pm 2 days		+ 7 days	\pm 14 days
Informed consent ¹	X										
Inclusion/exclusion criteria	X										
Demographics	X										
Medical history ²	X	X									
Patient height	X										
Patient weight	X	X		X	X	X	X	X	X		
Body Surface Area (BSA) ³	X										
Physical examination, full including vital signs ⁴	X								X		

Activity/Assessment	Screening	Cycle 1				Cycle 2		Cycles ≥ 3	End-of-Treatment (EoT) Visit	Safety Follow-up Call	Durability of Response and Survival Follow-up ¹⁵
	Day -21 to Day -1	Day 1	Day 3 ¹⁴	Day 8	Day 15	Day 1	Day 15	Day 1	≤ 14 Days Post Last Dose	30 Days Post-Last Dose	Every 3 mo.
		-1 day	+1 day	± 1 day	± 1 day	± 2 days	± 2 days	± 2 days		+ 7 days	± 14 days
Physical examination, symptom-directed, including vital signs ⁴		X		X	X	X	X	X			
ECOG ⁵	X					X		X	X		
Echocardiogram or MUGA ⁶	X										
12-lead ECG	X								X		
Ophthalmic exam ⁷	X								X		
Clinical Labs											
Urinalysis ⁵	X								X		
CBC with differential ⁵	X			X	X	X	X	X	X		
TSH ⁵	X								X		
Complete serum chemistry ⁵	X					X		X	X		

Activity/Assessment	Screening	Cycle 1				Cycle 2		Cycles ≥ 3	End-of-Treatment (EoT) Visit	Safety Follow-up Call	Durability of Response and Survival Follow-up ¹⁵
	Day -21 to Day -1	Day 1	Day 3 ¹⁴	Day 8	Day 15	Day 1	Day 15	Day 1	≤ 14 Days Post Last Dose	30 Days Post-Last Dose	Every 3 mo.
		-1 day	+1 day	± 1 day	± 1 day	± 2 days	± 2 days	± 2 days		+ 7 days	± 14 days
Limited serum chemistry				X	X		X				
Coagulation tests ⁵	X								X		
Serum hCG pregnancy test ⁸	X					X (D1 of each cycle only)		X (D1 of each cycle only)	X		
C-reactive protein	X	X				X		X	X		
Multiple Myeloma Assessments											
SPEP and serum protein immunofixation ⁹	X	X				X		X	X		X
UPEP (24-hr urine for total protein) and urine protein immunofixation ⁹	X	X				X		X	X		X
Quantitative Ig levels ⁹	X	X				X		X	X		X

Activity/Assessment	Screening	Cycle 1				Cycle 2		Cycles ≥ 3	End-of-Treatment (EoT) Visit	Safety Follow-up Call	Durability of Response and Survival Follow-up ¹⁵
	Day -21 to Day -1	Day 1	Day 3 ¹⁴	Day 8	Day 15	Day 1	Day 15	Day 1	≤ 14 Days Post Last Dose	30 Days Post-Last Dose	Every 3 mo.
		-1 day	+1 day	± 1 day	± 1 day	± 2 days	± 2 days	± 2 days		+ 7 days	± 14 days
Serum FLC ⁹	X	X			X	X	X	X	X		X
β ₂ -microglobulin	X								X		
Skeletal survey ¹⁰	X					(X)		(X)	X		(X)
Plasmacytoma assessment ¹¹	X					(X)		(X)	X		(X)
CCI											
CCI											
FACT-MM questionnaire	X					X		X	X		
Study treatment dosing		Selinexor 80 mg + dexamethasone 20 mg (both twice weekly) for 4 weeks (each week) of 4-week cycles									
Adverse events ¹⁶	X	X	X	X	X	X	X	X	X	X	
Concomitant medications	X	X	X	X	X	X	X	X	X		

Activity/Assessment	Screening	Cycle 1				Cycle 2		Cycles ≥ 3	End-of-Treatment (EoT) Visit	Safety Follow-up Call	Durability of Response and Survival Follow-up ¹⁵
	Day -21 to Day -1	Day 1	Day 3 ¹⁴	Day 8	Day 15	Day 1	Day 15	Day 1	≤ 14 Days Post Last Dose	30 Days Post-Last Dose	Every 3 mo.
		-1 day	+1 day	± 1 day	± 1 day	± 2 days	± 2 days	± 2 days		+ 7 days	± 14 days
Nutritional consultation	X										
Telephone contact ¹⁴			X							X	X
Antineoplastic therapy after EoT									X	X	X

(X) indicates that additional information is provided in the footnotes. Merged cells indicate that the procedure may be performed during either Screening or the CID1 visit.

Abbreviations: BSA = body surface area; ECG = electrocardiogram; ECOG = Eastern Cooperative Oncology Group; EoT = End of Treatment; Ig = immunoglobulin; MM = multiple myeloma; SPEP = serum protein electrophoresis; UPEP = urine protein electrophoresis; CBC = complete blood count; FLC = free light chain.

¹ Prior to the first study-specific measure.

² Including details of all prior anti-myeloma therapies. Includes baseline symptoms as well as a detailed history of prior cancer therapies, especially MM therapies, including start and stop dates, disease progression during or after therapy, as well as discontinuations due to intolerability or any other serious illness.

³ Body Surface Area (BSA) will be calculated by *Dubois 1916* or *Mosteller 1987* method during Screening and prior to any dose escalation. No patient may receive a dose of selinexor > 70 mg/m².

⁴ Complete physical examination (PE) during Screening and EoT visit. Limited PEs during the study should be symptom directed. All PEs to include vital signs (blood pressure, pulse and body temperature).

⁵ The following procedures may be performed at Screening or pre-dose on CID1 and as shown in the Schedule during the study: ECOG performance assessment, echocardiogram or MUGA scan, 12-lead ECG, ophthalmic exam, urinalysis, CBC with differential, TSH, complete serum chemistry, coagulations tests, and nutritional consultation.

⁶ Echocardiogram or MUGA scan at Screening and as clinically indicated during the study.

⁷ A full ophthalmic examination will include, prior to dilation, best corrected visual acuity, slit lamp examination including tonometry, following dilation; funduscopy and slit lamp to document lens clarity.

- ⁸ For females of childbearing potential; negative serum hCG pregnancy test must be obtained within 3 days before the first dose of study treatment. Pregnancy testing (serum hCG or urine) is also required for females of childbearing potential prior to dosing on Day 1 of Cycles ≥ 2 and at the EoT Visit (serum hCG). Pregnancy testing may also be performed as clinically indicated during the study.
- ⁹ Response criteria include SPEP, UPEP (24-hr urine), serum and urine immunofixation, quantitative Ig levels, and serum FLC assay on C1 D1 and must be taken either on Day -1 or pre-dose on C1D1. The assessments must be repeated at the time of disease progression or suspected response in order to confirm response. Note: For patients who achieve CR or sCR, as assessed by the local lab, assessments will be confirmed by a central lab using portions of the samples collected. See the *Study Manual* for additional information.
- ¹⁰ Skeletal survey to be performed using x-rays per institutional guidelines. If x-rays are used, they should include a lateral radiograph of skull, anteroposterior and lateral views of the spine, and anteroposterior views of the pelvis, ribs, femora, and humeri. If clinically appropriate, MRI, CT, or PET/CT, with tumor measurements, may be used instead of, or in addition to, x-rays. If bone lesions or plasmacytomas are observed at baseline, their number and size should be recorded in the CRF. Bone lesions and/or plasmacytomas seen at baseline using imaging should be assessed as clinically appropriate per Investigator's discretion during the study. Skeletal survey results will be read by the local laboratory.
- ¹¹ If plasmacytomas are detected at baseline by PE, they should be measured and recorded, and re-assessed during the PE on Day 1 of each cycle, EoT visit, and every 3 months (if clinically appropriate) during follow-up.
- ¹² [REDACTED]
- ¹³ [REDACTED]
- ¹⁴ Telephone call (or visit) with patient to evaluate supportive care medications, concomitant medications and adverse events, and to adjust supportive care as appropriate. The telephone contact with the patient must take place on C1D3 (following administration of first dose of selinexor on C1D1).
- ¹⁵ After treatment discontinuation, if possible, for patients who are not progressing, SPEP with serum immunofixation, UPEP (24 hr.) with urine protein immunofixation, serum FLC, and quantitative Ig levels (and physical examinations and imaging for bone lesions and plasmacytomas, if clinically appropriate) should be performed every 3 months for 1 year to assess durability of response. If these assessments cannot be performed, and for patients with PD, a telephone call will be made to the patient (or the patient's family) every 3 months for one year to inquire about the patient's survival, MM status, well-being, and information on any antineoplastic therapies utilized since discontinuation of selinexor study treatment.
- ¹⁶ Serious adverse events that occur after signing patient signs the ICF (including prior to first dose on C1D1) and adverse events that occur after first dose on C1D1.

7.2. Appendix II: Thresholds/Range Analyses for Select Laboratory, Vital Sign, and ECG Parameters

Table 7-2 Definitions of thresholds and ranges for selected laboratory, vital signs, and ECG parameters.

Parameter	Thresholds/Ranges	Basis or Comments
Clinical Chemistry		
CPK	>ULN - $\leq 2.5 \times$ ULN >2.5 - $\leq 5 \times$ ULN >5 - $\leq 10 \times$ ULN >10 x ULN	CTCAE grades 1-4
Creatinine	>ULN - $\leq 1.5 \times$ ULN >1.5 - $\leq 3.0 \times$ ULN >3.0 - $\leq 6.0 \times$ ULN >6.0 x ULN	CTCAE grades 1-4
Blood Urea Nitrogen	>ULN - $\leq 1.5 \times$ ULN >1.5 - $\leq 3.0 \times$ ULN >3.0 - $\leq 6.0 \times$ ULN >6.0 x ULN	Same criteria as creatinine No CTCAE
Chloride	<LLN >ULN	No CTCAE
Sodium	Hyponatremia <LLN - ≥ 130 mmol/L <130 - ≥ 120 mmol/L <120 mmol/L	CTCAE grade 1, 3, 4 (No CTCAE grade 2)
	Hypernatremia >ULN - ≤ 150 mmol/L >150 mmol/L - ≤ 155 mmol/L >155 mmol/L - ≤ 160 mmol/L >160 mmol/L	CTCAE grade 1-4

Potassium	Hypokalemia <LLN - \geq 3.0 mmol/L <3.0 - \geq 2.5 mmol/L <2.5 mmol/L	CTCAE grade 1&2, 3, 4 (Grade 1 and 2 are the same)
	Hyperkalemia >ULN - \leq 5.5 mmol/L >5.5 - \leq 6.0 mmol/L >6.0 - \leq 7.0 mmol/L >7.0 mmol/L	CTCAE grade 1-4
Total Cholesterol	>ULN - \leq 7.75 mmol/L >7.75 - \leq 10.34 mmol/L >10.34 - \leq 12.92 mmol/L >12.92 mmol/L	CTCAE grade 1-4
Triglycerides	>1.71 - \leq 3.42 mmol/L >3.42 - \leq 5.7 mmol/L >5.7 - \leq 11.4 mmol/L >11.4 mmol/L	CTCAE grade 1-4
Glucose	Hypoglycemia <LLN - \geq 3.0 mmol/L <3.0 - \geq 2.2 mmol/L <2.2 - \geq 1.7 mmol/L <1.7 mmol/L	CTCAE grade 1-4
	Hyperglycemia >ULN - \leq 8.9 mmol/L >8.9 - \leq 13.9 mmol/L >13.9 - \leq 27.8 mmol/L >27.8 mmol/L	CTCAE grade 1-4
Albumin	<LLN - \geq 30 g/L <30 - \geq 20 g/L <20 g/L	CTCAE grade 1-3

Amylase	>ULN - $\leq 1.5 \times$ ULN >1.5 - $\leq 2.0 \times$ ULN >2.0 - $\leq 5.0 \times$ ULN >5.0 x ULN	CTCAE grade 1-4
Lipase	>ULN - $\leq 1.5 \times$ ULN >1.5 - $\leq 2.0 \times$ ULN >2.0 - $\leq 5.0 \times$ ULN >5.0 x ULN	CTCAE grade 1-4
Direct bilirubin	>ULN - $\leq 1.5 \times$ ULN >1.5 - $\leq 2 \times$ ULN >2 - $\leq 3 \times$ ULN >3 - $\leq 10 \times$ ULN >10 x ULN	Same Criteria as Total Bilirubin No CTCAE Not in DILI Guidance
GGT	>ULN - $\leq 2.5 \times$ ULN >2.5 - $\leq 5.0 \times$ ULN >5.0 - $\leq 20.0 \times$ ULN >20.0 x ULN	CTCAE grade 1-4
Total protein	<LLN >ULN	No CTCAE
LDH	<LLN >ULN	No CTCAE
Calcium	Hypercalcemia >ULN - ≤ 2.9 mmol/L >2.9 - ≤ 3.1 mmol/L >3.1 - ≤ 3.4 mmol/L >3.4 mmol/L	CTCAE grade 1-4
	Hypocalcemia <LLN - ≥ 2.0 mmol/L <2.0 - ≥ 1.75 mmol/L <1.75 - ≥ 1.5 mmol/L <1.5 mmol/L	CTCAE grade 1-4
Magnesium	Hypermagnesemia >ULN - ≤ 1.23 mmol/L	CTCAE grade 1, 3, 4

	
>1.23 – ≤ 3.30 mmol/L >3.30 mmol/L
	No CTCAE grade 2
	
Hypomagnesemia <LLN - ≥ 0.5 mmol/L <0.5 – ≥ 0.4 mmol/L <0.4 – ≥ 0.3 mmol/L <0.3 mmol/L
	CTCAE grade 1-4
Bicarbonate	
<LLN >ULN
	No CTCAE
Inorganic phosphate	
Hypophosphatemia <LLN - ≥ 0.8 mmol/L <0.8 – ≥ 0.6mmol/L <0.6 – ≥ 0.3 mmol/L <0.3 mmol/L
	CTCAE grade 1-4
Vitamins: A, D (25-hydroxy), E, K, B12	<LLN	No CTCAE
LDL	>ULN	No CTCAE
HDL	<LLN	No CTCAE
ALT	
>ULN - ≤ 3 xULN >3 – ≤ 5 xULN >5 – ≤ 8 xULN >8 – ≤ 20.0 xULN >20.0 x ULN
	Per FDA DILI Guidance Jul 2009 and CTCAE
AST	
>ULN - ≤ 3 xULN >3 – ≤ 5 xULN >5 – ≤ 8 xULN >8 – ≤ 20.0 xULN >20.0 x ULN
	FDA DILI Guidance and CTCAE
ALT or AST	ALT>3xULN or AST>3xULN	FDA DILI Guidance

Alkaline Phosphatase	>ULN - \leq 1.5xULN >1.5 - \leq 2.5 xULN >2.5 - \leq 5.0 x ULN >5.0 - \leq 20.0 x ULN >20.0 x ULN	FDA DILI Guidance and CTCAE
Total Bilirubin	>ULN - \leq 1.5 x ULN >1.5 - \leq 2 x ULN >2 - \leq 3 x ULN >3 - \leq 10 x ULN >10 x ULN	FDA DILI Guidance and CTCAE
ALT and Total Bilirubin	ALT>3xULN and TBILI>2xULN	FDA DILI Guidance Jul 2009
AST and Total Bilirubin	AST>3xULN and TBILI>2xULN	FDA DILI Guidance Jul 2009
(ALT or AST) and Total Bilirubin	(ALT>3xULN or AST>3xULN) and TBILI>2xULN	FDA DILI Guidance Jul 2009
Hematology		
WBC	WBC decreased <LLN - \geq 3.0 x 10e9 /L <3.0 - \geq 2.0 x 10e9 /L <2.0 - \geq 1.0 x 10e9 /L <1.0 x 10e9 /L	CTCAE grade 1-4
	Leukocytosis >100 x 10e9 /L	CTCAE grade 3 (only Grade available)
Lymphocytes	Lymphocyte decreased <LLN - \geq 0.8 x10e9 /L <0.8 - \geq 0.5 x10e9 /L <0.5 - \geq 0.2 x10e9 /L <0.2 x10e9 /L	CTCAE grade 1-4
	Lymphocyte increased >4 - \leq 20 x10e9/L >20 x10e9/L	CTCAE grade 2, 3 (only Grades available)
Neutrophils	Neutrophil decreased <LLN - \geq 1.5 x10e9 /L	CTCAE grade 1-4

	
<1.5 – ≥ 1.0 x10e9 /L
 
<1.0 – ≥ 0.5 x10e9 /L
 
<0.5 x10e9 /L
	
Monocytes	>ULN	No CTCAE
Basophils	>ULN	No CTCAE
Eosinophils	>ULN	No CTCAE
Hemoglobin	
Hgb decreased (anemia)
 
<LLN - ≥ 100 g/L
 
<100 – ≥ 80 g/L
 
< 80 g/L
	CTCAE grade 1-3
	
Hgb increased
 
>ULN - ≤ 20 g/L above ULN
 
>20 g/L above ULN - ≤ 40 g/L above ULN
 
>40 g/L above ULN
	CTCAE grade 1-3
RBC	
<LLN
 
>ULN
	No CTCAE
Platelets	
Platelet decreased
 
<LLN - ≥ 75.0 x 10e9 /L
 
<75.0 – ≥ 50.0 x 10e9 /L
 
<50.0 – ≥ 25.0 x 10e9 /L
 
<25.0 x 10e9 /L
	CTCAE grade 1-4
	
Platelet increased
 
>ULN
	No CTCAE available
Mean corpuscular hemoglobin	
<LLN
 
>ULN
	No CTCAE

Mean corpuscular hemoglobin concentration	<LLN >ULN	No CTCAE
Mean corpuscular volume	<LLN >ULN	No CTCAE
Reticulocytes	<LLN >ULN	No CTCAE
Coagulation		
Activated partial thromboplastin time (PTT)	>ULN - $\leq 1.5 \times$ ULN >1.5 - $\leq 2.5 \times$ ULN >2.5 x ULN	CTCAE grade 1-3
Prothrombin time (PT) International Normalized Ratio (INR)	>ULN - $\leq 1.5 \times$ ULN >1.5 - $\leq 2.5 \times$ ULN >2.5 x ULN	CTCAE grade 1-3
ECGs		
HR	Bradycardia <50 bpm Decrease from baseline ≥ 10 bpm Decrease from baseline ≥ 20 bpm <50 bpm and decrease from baseline ≥ 10 bpm <50 bpm and decrease from baseline ≥ 20 bpm	Per HV grade 2, 3, plus shift change
	Tachycardia >120 bpm Increase from baseline ≥ 20 bpm >120 bpm and increase from baseline ≥ 20 bpm	Per HV grade 1, 2, 3, plus shift change
PR	≥ 240 ms ≥ 200 ms and increase from baseline ≥ 40 ms ≥ 200 ms and increase from baseline ≥ 100 ms	

QRS	>120 ms Increase from baseline ≥ 20 ms Increase from baseline ≥ 40 ms	
QTc	>450 ms (Male) >470 ms (Female) ≥ 500 ms Increase from baseline >10 ms Increase from baseline >30 ms Increase from baseline >60 ms	
Vital Signs		
HR	Same PCS as above in ECG category	
SBP	SBP increased >140 mmHg >160 mmHg >10 mmHg increase from baseline >20 mmHg increase from baseline >160 mmHg & >10 mmHg increase from baseline >160 mmHg & >20 mmHg increase from baseline	
	SBP decrease <100 mmHg >10 mmHg decrease from baseline >20 mmHg decrease from baseline <100 mmHg and >10 mmHg decrease from baseline	Per HV grade 1, 3, plus shift change

	<100 mmHg and >20 mmHg decrease from baseline	
DBP	DBP increased >90 mmHg >100 mmHg >5 mmHg increase from baseline >10 mmHg increase from baseline >100 mmHg and >5 mmHg increase from baseline >100 mmHg and >10 mmHg increase from baseline	
	DBP decreased <60 mmHg >5 mmHg decrease from baseline >10 mmHg decrease from baseline <60 mmHg and >5 mmHg decrease from baseline <60 mmHg and >10 mmHg decrease from baseline	
Weight	Weight gain ≥5 % increase from baseline ≥10 % increase from baseline ≥ 20% increase from baseline	CTCAE grade 1-3
	Weight loss ≥5 % decrease from baseline ≥10 % decrease from baseline ≥ 20% decrease from baseline	CTCAE grade 1-3
